2.7.1.1 Adverse events of special interest (AESI) and potential risks

The following specific safety topics will be summarized separately in addition to the above analysis:

- AESI
 - Serious hypotension
 - o Serious hypersensitivity reactions
 - Serious injection site reactions
 - Severe tachycardia
 - Severe acute bradycardia
 - Serious presyncope/syncope
- Potential risks:
 - Hypotension
 - o Tachycardia
 - o Bradycardia
 - Hypersensitivity reactions
 - Injection site reactions
 - Immunogenicity
- Other safety topics

- Renal toxicity
- Hepatotoxicity

The sets of terms, pertaining either to MedDRA or to NMQ or to CMQ, that are used to search the database to retrieve cases of interest that relate to the safety topics listed above are stored (or alternatively "summarize") in the Case Retrieval Strategy (eCRS). The latest version of the eCRS at the time of database lock will be used.

The following standard analyses will be provided for all the listed safety topics (

- Incidence (absolute and relative frequency) rates in terms of participant regardless of causal relationship to study drug for randomized treatment period, by treatment group.
- Exposure-adjusted incidence rates per 100 patient years regardless of study drug relationship for randomized treatment period, by treatment
- Analysis for time-to-first selected safety topic of interest by treatment group will be performed for randomized treatment period using Kaplan-Meier estimates
- Listing of AEs by participant with AESI and risk information.

In addition to the above, the analysis specified below will be provided for the safety topics that are listed in Table 2-3.

Table 2-3 AESIs and potential risks with additional analysis

Safety topic	Definitions	Analysis and additional criteria for characterizing selected AEs
Hypotension	Hypotension [STANDARD] (NMQ)	Distribution of TEAE by pre-defined subgroups (as per Table 2-1)
Tachycardia	ADR Tachycardia [ADR_STD] (NMQ)	Distribution of TEAE by pre-defined subgroups (as per Table 2-1)
Bradycardia	ADR Heart rate decreased [ADR_STD] (NMQ)	Distribution of TEAE by pre-defined subgroups (as per Table 2-1)
Injection site reactions	ADR Injection site reaction [ADR_STD] (NMQ)	Distribution of TEAE by the following subgroups: a. age <60 vs. ≥60 years b. age ≤median vs. > median c. sex d. region e. race f. history of diabetes g. weight ≤median vs. > median h.
Hypersensitivity reactions	(Anaphylactic/anaphylactoid shock conditions (SMQ) OR Anaphylactic reaction (SMQ) OR Hypersensitivity other than administration site reactions [XXB750] (NMQ))	Distribution of TEAE by the following subgroups: a. age <60 vs. ≥60 years b. age ≤median vs. > median c. sex d. region

		e. race f. history of diabetes
		g. weight ≤media n vs. > median
	AU	h.
	All serious and non-serious TEAE in participants with at least one positive	Distribution of TEAE by (as per Table 2-1)
Serious	Only SAE: ADR Hypotension	Distribution of TEAE by pre-defined
hypotension	[ADR_STD] (NMQ)	subgroups (as per Table 2-1)
Serious	Only SAE:	Distribution of TEAE by the following
hypersensitivity reactions	(Anaphylactic/anaphylactoid shock conditions (SMQ) OR Anaphylactic	subgroups:
TCGCIIOTIS	reaction (SMQ) OR Hypersensitivity	a. age <60 vs. ≥60 years
	other than administration site reactions	b. age ≤median vs. > median c. sex
	[XXB750] (NMQ))	d. region
		e. race
		f. history of diabetes
		g. weight ≤median vs. > median
		h
Serious injection site	Only SAE: ADR Injection site reaction [ADR_STD] (NMQ)	Distribution of TEAE by the following subgroups:
reactions	[/\text{\tint{\text{\tint{\text{\tint{\text{\tint{\text{\tint{\text{\tint{\text{\text{\text{\text{\text{\tin\text{\text{\text{\text{\text{\text{\text{\text{\text{\texit{\text{\text{\text{\text{\text{\text{\text{\text{\text{\text{\tex{\tex	a. age <60 vs. ≥60 years
		b. age ≤median vs. > median
		c. sex
		d. region
		e. race
		f. history of diabetes
		g. weight ≤median vs. > median
		h.
Severe tachycardia	Only severe AE: ADR Tachycardia [ADR_STD] (NMQ)	Distribution of TEAE by pre-defined subgroups (as per Table 2-1)
Severe acute	Only severe AE: ADR Heart rate	Distribution of TEAE by pre-defined
bradycardia	decreased [ADR_STD] (NMQ)	subgroups (as per Table 2-1)
Serious	Only SAE: ADR Presyncope	Distribution of TEAE by pre-defined
presyncope/syn	[ADR_STD] (NMQ) OR ADR	subgroups (as per Table 2-1)
cope	Depressed level of consciousness	·
	[ADR_STD] (NMQ) OR ADR Loss of consciousness [ADR_STD] (NMQ)	

2.7.2 Deaths

Participants that died during the study period will be reported separately for run-in period, randomization period, randomized treatment period and safety follow-up. Deaths will be

summarized by actually received treatment group to present number and percentage of participants that died. In addition, listings will be provided for participants that died.

The analysis will consider all participants in the Safety set (SAF) for reported deaths during the randomization period while deaths during the run-in period will be reported based on participants in the Run-in set (RIS).

2.7.3 Laboratory data

For each laboratory parameter, evaluations will be summarized by visit and actually received treatment group by presenting summaries (n, mean, standard deviation, median, minimum and maximum) for actual and change from baseline values for both run-in and randomization period. The summary will be provided separately for biochemistry and hematology laboratory parameters. Central laboratory data will be used for the summaries.

Shift tables based on the standard ranges for each laboratory parameter (biochemistry and hematology) will be provided by treatment group at each visit for the randomization period to present incidence of transitions from a baseline high, normal or low laboratory value to a maximum post-baseline high, normal or low value. In addition to these analyses, laboratory parameter values will be listed for each participant by scheduled assessment visit and treatment group.

The number and percentage of participants with clinically notable laboratory results after baseline will be presented in accordance with Table 2-4, by visit and overall, for randomized treatment period and other periods as appropriate.

Table 2-4 Clinically notable laboratory values and vital signs

Parameter	Clinical notable criteria
Hematology	
Red blood cell count	> 50% increase AND value > ULN
	> 30% decrease AND value < LLN
Hemoglobin	> 50% increase AND value > ULN
	either (> 30% decrease AND value < LLN) OR value < 8.0 g/dL
Hematocrit	> 50% increase AND value > ULN
	> 30% decrease AND value < LLN
White blood cell count	value > 100,000 cells/mm³ (unit equivaleng to 10E6/L)
	value < 2000 cells/mm³ (unit equivaleng to 10E6/L)
Platelet count	value < 50,000 platelets/mm³ (unit equivaleng to 10E6/L)
Blood chemistry	
Alkaline phosphatase	value > 5 x ULN if baseline was normal OR value > 5 x baseline if baseline was abnormal
ALT (SGPT)	value > 5 x ULN if baseline was normal OR value > 5 x baseline if baseline was abnormal
AST (SGOT)	value > 5 x ULN if baseline was normal OR value > 5 x baseline if baseline was abnormal
Total bilirubin	value > 3 x ULN if baseline was normal OR value > 3 x baseline if baseline was abnormal

SAP

* **	
Doromotor	Clinical notable evitoria
Parameter BUN	Clinical notable criteria ≥ 50% increase
Creatinine	≥ 50% increase
Potassium	value > 6.0 mmol/L
	value < 3.0 mmol/L
Chloride	> 115 mEq/L
	< 90 mEq/L
Calcium	corrected serum calcium > 3.1 mmol/L
	corrected serum calcium < 1.75 mmol/L
Uric acid	> 50% increase
Plasma glucose	> 25% increase
	value < 40 mg/dL
Blood pressure increase (mean mean mean mean mean mean mean mean	
Mean sitting office SBP (mmHg)	> 180 mmHg
Mean sitting office DBP (mmHg)	> 110 mmHg
Blood pressure decrease (mean m	neasurement)
1. Mean sitting office SBP (mmHg)	< 110 mmHg
2. Mean sitting office DBP (mmHg)	< 70 mmHg
3. Criteria 1 OR 2	Participants meeting either criterion 1 OR criterion 2
4. ABPM day time mean SBP (mmHg)	< 110 mmHg
5. ABPM day time mean DBP (mmHg)	< 70 mmHg
6. Criteria 4 OR 5	Participants meeting either criterion 4 OR criterion 5
7. ABPM night time mean SBP (mmHg)	< 90 mmHg
8. ABPM night time mean DBP (mmHg)	< 55 mmHg
9. Criteria 7 OR 8	Participants meeting either criterion 7 OR criterion 8
10. ABPM mean 24 hours SBP (mmHg)	< 105 mmHg
11. ABPM mean 24 hours DBP (mmHg)	< 65 mmHg
12. Criteria 10 OR 11	Participants meeting either criterion 10 OR criterion 11
13. Any one criteria	Participants meeting any one of the criteria 1 to 12
He aut mate't in anne :	
Heart rate* increase	. 400
Pulse (bpm)	> 100
Heart rate* decrease	
Pulse (bpm)	1. < 60
	0

2. < 50

Orthostatic hypotension

Parameter	Clinical notable criteria
Systolic blood pressure (mm Hg) minute after standing	≥ 20 mmHg reduction from corresponding mean measurement in sitting position
Diastolic blood pressure (mm Hg) minute after standing	≥ 10 mmHg reduction from corresponding mean measurement in sitting position
3. Systolic blood pressure (mm Hg) 3 minutes after standing	≥ 20 mmHg reduction from corresponding mean measurement in sitting position
4. Diastolic blood pressure (mm Hg) 3 minutes after standing	≥10 mmHg reduction from corresponding mean measurement in sitting position
5. Criteria 1 OR 2	Participants meeting either criterion 1 OR criterion 2
6. Criteria 3 OR 4	Participants meeting either criterion 3 OR criterion 4
7. Criteria 5 OR 6	Participants meeting either criterion 5 OR criterion 6
Liver function tests	
ALT (SGPT) OR AST (SGOT)	1. value > 3 x ULN
	2. value > 5 x ULN
	3. value > 8 x ULN
	4. value > 10 x ULN
	5. value > 20 x ULN
ALT (SGPT) OR AST (SGOT) AND	1. ALT or AST > 3 x ULN and TB > 1.5 x ULN
Total bilirubin (TB)	2. ALT or AST > 3 x ULN and TB > 2 x ULN
	3. ALT or AST > 5 x ULN and TB > 2 x ULN
	4. ALT or AST > 8 x ULN and TB > 2 x ULN
	5. ALT or AST > 10 x ULN and TB > 2 x ULN
	6. ALT or AST > 20 x ULN and TB > 2 x ULN
Alkaline phosphatase	1. > 2 x ULN
	2. > 3 x ULN
	3. > 5 x ULN
Total bilirubin	1. > 1.5 x ULN
	2. > 2 x ULN
AH 15 1 1 1 (ALE) AND	3. > 3 x ULN
Alkaline phosphatase (ALP) AND TB	1. ALP > 3 x ULN AND TB > 2 x ULN
	2. ALP > 5 x ULN AND TB > 2 x ULN
ALT (SGPT) OR AST (SGOT) AND Total bilirubin (TB) AND Alkaline	1. ALT OR AST > 3 x ULN AND TB > 2 x ULN AND ALP ≤ 2 x ULN
phosphatase (ALP)	2. ALT OR AST > 3 x ULN AND TB > 2 x ULN AND ALP ≤ 2 x ULN OR reported H"s Law case
	3. TB > 3 x ULN AND AST OR ALT \leq 3 x ULN AND ALP \leq 1.5 x ULN
	4. ALP > 3 x ULN AND AST AND ALT AND TB are within normal range
Laboratorial and clinical associations	ALT OR AST > 3 x ULN AND (Nausea OR Vomiting OR Fatigue OR General malaise OR Abdominal pain OR (Rash AND Eosinophilia))

Parameter	Clinical notable criteria
Renal function tests	
eGFR	1. > 25% decrease
	2. > 40% decrease
	3. > 50% decrease
	4. > 30 mL/min/1.73m ² decrease
	5. Participants meeting any of the criteria 1 to 4 above
Creatinine	1. ≥ 0.3 mg/dL increase
	2. ≥1.5 to ≤ 1.9 x baseline
	3. >1.9 to ≤ 2.9 x baseline
	4. > 2.9 x baseline
	5. ≥ 4.0 mg/dL
	6. Participants meeting either criterion 1 OR 2 above
	7. Participants meeting either criterion 4 OR 5 above
New onset of proteinuria	Urine protein ≥ 300 mg/dL
New onset of hematuria	Urine hemoglobin ≥ 1 mg/dL

ULN: upper limit of the normal range; LLN: lower limit of the normal range; SBP: systolic blood pressure; DBP: diastolic blood pressure; ABPM: ambulatory blood pressure measurement; Increases and decreases of parameters as mentioned in the table are from baseline; * Heart Rate: increase or decrease is based on 24hr mean measurement of ABPM.

Participants with liver function tests (ALT, AST, ALP, Total Bilirubin) and renal-related parameters falling within predefined categories of elevations (new and worsened [i.e. those existent before, and that worsened after randomization] elevations) will be summarized by treatment group in accordance with Table 2-4 for both run-in period, randomized treatment period and randomization period. Descriptive summaries by presenting count and percentage of participants with each type of Liver and Renal event in addition to graphical summaries will be displayed, as applicable.

For the rate change in eGFR during randomized treatment period, the eGFR slope will be estimated from a repeated measures ANCOVA model including treatment, number of background antihypertensive medications (=3 vs>3), region, time (when the eGFR is assessed in weeks), and treatment-by-time as fixed effects with random intercept and slope (time) and a common unstructured covariance. The least-square means of slopes for within and between treatment groups, and the corresponding two-sided 95% confidence intervals will be provided.

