8.3 Efficacy assessments

8.3.1 Ambulatory blood pressure monitoring

The first 24-hour ABPM assessment will be performed at Visit 30 (End of Run-in) and after the participant has met office BP criteria (i.e. msSBP < 180 mmHg and msDBP <110 mmHg). The second and third ABPM assessments will be performed at weeks 9 and week 12 (visit 160 and visit 170/EOT respectively), or earlier in the case of premature permanent discontinuation of blinded study drugs. ABPM assessments may be repeated at any of the visits listed above if there is a quality control finding.

ABPM Procedures

Patients should take their background medications in the clinic witnessed by the investigator or designee (and study medication when applicable) prior to attaching the ABPM device. The ABPM device should be attached to the non-dominant arm of the participant. The application/verification procedures consist of taking several readings using manual prompts to verify that the ABPM device is functioning properly and that no error codes are obtained during the application process. The verification process is not intended for comparison to the clinic reading but rather for confirming that the unit is working properly before prompting the 24-hour period to begin. Following the completion of the verification readings, the investigator or his/her staff would prompt an additional reading to identify the "Beginning of Test" time.

The ABPM unit will be automatically set to measure and record BP every 20 minutes during the day and every 30 minutes during the night.

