8.4.1 Physical examinations

Physical examinations will be performed by the investigator or his/her designee who are qualified to do so per local regulations/standards. A complete physical examination will include the examination of the general appearance, vital signs (blood pressure [SBP and DBP] and pulse), skin, neck (including thyroid), eyes, ears, nose, throat, lungs, heart, abdomen, back, lymph nodes, extremities, the vascular, and the neurological systems. If indicated based on medical history and/or symptoms, rectal, external genitalia, breast, and pelvic exams will be performed.

A short physical exam will include the examination of the general appearance and vital signs (blood pressure [SBP and DBP] and pulse). Refer to Table 1-2 for details of the type and frequency of the physical examination.

Information about all physical examinations performed must be included in the source documentation at the study site. Clinically relevant findings that are present before signing informed consent must be recorded on the appropriate CRF page that captures medical history. Significant findings made after signing informed consent which meet the definition of an Adverse Event must be recorded as an adverse event.

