8.4.2 Vital signs

Vital signs include BP and pulse measurements.

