9.4.2 Safety endpoints

For all safety analyses, the safety set will be used. All listings, figures and tables will be presented by treatment group.

Adverse events

All information obtained on adverse events will be displayed by treatment group.

The number (and percentage) of participants with treatment emergent adverse events (events started after the first dose of study medication or events present prior to start of double-blind treatment but increased in severity based on preferred term) will be summarized in the following ways:

- by treatment, primary system organ class and preferred term.
- by treatment, primary system organ class, preferred term and maximum severity.
- by treatment, Standardized Medical Dictionary for Regulatory Activities (MedDRA) Query (SMQ) and preferred term.

Separate summaries will be provided for study medication related adverse events, death, serious adverse events, other significant adverse events leading to discontinuation, and adverse events leading to dose adjustment.

The number (and proportion) of participants with adverse events of special interest and related to potential risks (as per the Investigator's Brochure) will be summarized by treatment.

A participant with multiple adverse events within a primary system organ class is only counted once towards the total of the primary system organ class.

Adverse events which will be counted for a specific treatment period are those which are treatment-emergent. These events are those with an onset after the start of the treatment period, or which were present prior to the start of the treatment period but increased in severity, changed from being not suspected to being suspected of study treatment relationship, or developed into SAEs after the start of the treatment period.

More details on the analysis of AE will be described in the Statistical Analysis Plan (SAP).

Vital signs

Summary statistics will be provided by treatment and visit for all vital signs, as well as for the proportion of participants presenting with clinically notable abnormal values. Graphical displays of the values of selected vital signs over time may be provided by treatment group.

More details on the analysis of vital signs will be described in the Statistical Analysis Plan (SAP).

12-lead ECG

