The randomized treatment period begins at the time of randomization and ends with the max(end of treatment (EOT) disposition, Week 12 EOT visit date). During the randomized treatment period, participants will return for scheduled clinic visits. For all related safety analyses, randomized treatment starts with the first administration of randomized, double-blind study drug.

Safety follow-up period

The safety follow-up period begins one day after max(end of treatment (EOT) disposition, Week 12 EOT visit date), and ends on the date of EOS. For participants whose EOS visit is on/before Week 12 and for those who do not take study treatment at all during randomized treatment period, they should not have safety follow-up period calculated, i.e., start date and end date for safety follow-up should be missing.

Randomization period

The randomization period is the combination of the randomized treatment period and the safety follow-up period.

Study exposure

The study exposure means the exposure for the randomization period. The duration of study exposure (days) is defined as the date of end of study minus the date of randomization plus one.

Baseline for randomized treatment period

Only assessments performed prior to first dose of randomized treatment period are considered for baseline. Unless specified otherwise, baseline for the randomized treatment period is defined as the measurement obtained at the end of run in (Visit 30) or randomization visit (Visit 100) whichever occurs last, or the measurement obtained at an earlier visit (scheduled or unscheduled) which was closest to the Visit 30/Visit 100, if Visit 30/Visit 100 measurement is missing.

For OBPM, baseline derivation is based on measurements eligible for analysis, as specified in Section 2.12.1

Baseline for randomization period

Randomization period is the total duration of randomized treatment period and the safety follow-up period. Therefore, the definition of baseline for randomization period will be the same as the baseline for randomized treatment period.

Baseline for safety follow-up period

Unless otherwise specified, baseline for safety follow-up period is defined as the measurement obtained at the EOT visit (Visit 170) or the measurement obtained closest to the EOT visit if the measurement at EOT is missing.

Baseline for run-in period

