2.7.4.2 Vital signs

Vital signs including weight, blood pressure and pulse measures will be summarized by treatment group and scheduled visit with standard summary statistics (mean, Q1, median, Q3, standard deviation, min, max), including changes from randomization baseline. Graphical mean plots with 95% CIs for these vital signs will also be provided. Change from baseline will only be summarized for participants with both baseline and post-baseline values and will be calculated as:

[figure not shown]
• change from baseline = post-baseline value – baseline value

The number and percentage of participants with clinically notable vital signs after baseline will be presented in accordance with Table 2-4 for randomized treatment period and randomization period, by visit and overall. The analysis will be based on SAF.

Apart from the above analyses, values for vital signs parameters will also be listed at a participant level by treatment group and visit for all participants in safety set (SAF).

Maximum and minimum of 24 hour blood pressure and heart rate values will be summarized by visit (mean, Q1, median, Q3, standard deviation, min, max) for randomized treatment period and for randomization period.

[figure not shown]

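### SAP Table 2-4 bases its only pulse criteria on the 24-hour ABPM mean, so the by-visit table of notable vital signs can count pulse at only 2 of 7 post-baseline visits

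*SAP*

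**What the plan says.** Protocol 8.4.2 is short: "Vital signs include BP and pulse measurements". Protocol 9.4.2 plans summaries by treatment and visit "for all vital signs, as well as for the proportion of participants presenting with clinically notable abnormal values". It sets no pulse limit and leaves further detail to the SAP.

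Pulse is taken at every physical examination, full or short. Protocol 8.4.1 states: "A short physical exam will include the examination of the general appearance and vital signs (blood pressure [SBP and DBP] and pulse".

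SAP 2.7.4.2 says that notable vital signs after baseline will be "presented in accordance with Table 2-4 for randomized treatment period and randomization period, by visit and overall". SAP 2.1.1 defines the longer of these periods: "The randomization period is the combination of the randomized treatment period and the safety follow-up period". The table therefore runs to Week 20.

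In SAP Table 2-4 the pulse limits (>100, <60 and <50 bpm) sit under two heart-rate headings marked with an asterisk. The footnote to that asterisk reads: "Heart Rate: increase or decrease is based on 24hr mean measurement of ABPM". The available SAP text and protocol Section 10.3.1 contain no other pulse limit.

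On the ABPM schedule, protocol 8.3.1 says: "The second and third ABPM assessments will be performed at weeks 9 and week 12 (visit 160 and visit 170/EOT respectively), or earlier". The exception that follows is premature permanent discontinuation of study drug.

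**The concern.** The SAP asks for a by-visit table, but its pulse criteria use a measurement that most of those visits do not have. The pulse taken in the clinic, which is what the protocol calls a vital sign, is never compared with the SAP's own limits.

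At stake is the number and percentage of participants per dose group beyond those limits in mid-interval, at the end of the first two dosing intervals and in follow-up. Heart rate is of some interest for this drug. Severe tachycardia and severe acute bradycardia are adverse events of special interest (protocol 8.6.6), and SAP 2.7 lists tachycardia and bradycardia as potential risks. Protocol 4.1 justifies the follow-up period by noting that XXB750 may be detectable for about 90 days after the last dose, and neither follow-up visit can give a pulse count.

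There is also a practical ambiguity. The row label uses the protocol's word for the examination measure, pulse, while the footnote points to ABPM. A programmer has to choose between them.

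**Working it through.** No sample size, power or alpha figure is involved. The check is a count of visits.

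**Inputs.** Visit days, physical examinations, ABPM and dosing come from protocol Table 1-2. Doses fall on Days 0, 28 and 56. The visit count uses the physical-examination row, because the vital-signs row shows a single mark in the available text and is probably a broken merged cell. Reading that row as covering all office visits gives the same seven post-baseline visits.

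| Visit | Planned day | Days since the preceding visit's dose | Pulse scheduled | ABPM scheduled | Pulse count under Table 2-4 |
|---|---|---|---|---|---|
| Week 2 | 14 | 14 - 0 = 14 | yes | no | no |
| Week 4 | 28 | 28 - 0 = 28 | yes | no | no |
| Week 8 | 56 | 56 - 28 = 28 | yes | no | no |
| Week 9 | 59 to 63 | 59 - 56 = 3 to 63 - 56 = 7 | yes | yes | yes |
| Week 12 | 84 | 84 - 56 = 28 | yes | yes | yes |
| Week 16 | 112 | 112 - 56 = 56 | yes | no | no |
| Week 20 | 140 | 140 - 56 = 84 | yes | no | no |

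For Weeks 4 and 8, where a dose is also due, the third column counts from the dose before that visit's own.

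**Results.**
- All post-baseline visits: 7 with pulse, 2 with ABPM, so 7 - 2 = 5 without a count.
- Treatment period: 5 - 2 = 3 without a count (Weeks 2, 4 and 8).
- Follow-up: 2 - 0 = 2 without a count (Weeks 16 and 20).

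**Can other ABPM recordings fill the gap?** Not as planned. SAP 2.1.1 says unscheduled ABPM is generally not used. An early-discontinuation ABPM belongs to the end-of-treatment visit (Visit 170) and does not supply the five missing visits. The overall count is likewise limited to participants with a Week 9 or Week 12/EOT recording.

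**With an office-pulse row**, the table could give a count at 7 of 7 post-baseline visits.

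**Separate wording check, liver rows.** The ALP, ALT, AST and total bilirubin rows of SAP Table 2-4 use a multiple of baseline when baseline was *abnormal*. Protocol Version 02 Table 10-2 says *abnormally high*. (The label of that table's first row is damaged in the available text; I read it as ALP.) Let b be a baseline below LLN and k the multiple, with k = 5 for ALP, ALT and AST and k = 3 for bilirubin. The SAP threshold is then k x b. Because b < LLN < ULN, k x b is always lower than k x ULN. A value inside the normal range is flagged if k x b < ULN, that is, if b < ULN/5 (ULN/3 for bilirubin). The documents give no reference ranges, so the number affected is unknown and may be zero.

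**The case against.** The strongest reply is that the SAP has simply chosen a measurement source. Protocol 9.4.2 promises a proportion, names no pulse limit or source, and defers to the SAP. A count by visit need not mean every parameter at every visit: blood-pressure criteria 4 to 12 in the same table are also ABPM-based and countable only at ABPM visits. This has force. A reader might infer that the SAP breaches the protocol, and the text does not go that far. What stands is that the clinic pulse, which protocol 8.4.2 names as a vital sign, has no notable criterion in the table, and the SAP gives no reason.

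A second reply is that little is lost. SAP 2.7.4.2 provides: "Vital signs including weight, blood pressure and pulse measures will be summarized by treatment group and scheduled visit with standard summary statistics", including minimum and maximum, with mean plots and participant listings. It also summarizes maximum and minimum 24-hour heart rate. ECG heart rate is summarized, with post-baseline ECGs at Weeks 12 and 20. Tachycardia and bradycardia are analysed through adverse-event searches with incidence, exposure-adjusted rates and Kaplan-Meier estimates. The Week 9 recording falls at what the estimand section calls the approximate peak state. So a reader who infers that heart rate goes unreported between doses or in follow-up would be wrong. Minimum and maximum show whether anyone crossed a limit, and the listings allow a hand count. What is missing is the planned count per arm at those visits.

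Three other stronger readings also fail:
- The 2-of-7 figure covers post-baseline visits only. Screening, run-in and end of run-in also have an examination.
- Blood pressure does not have both sources throughout. Only the BP-decrease rows do; the BP-increase rows are office-only and the orthostatic rows use sitting and standing readings.
- It cannot be said that the SAP lacks an office-pulse count anywhere. Section 2.7.4.3 and parts of 2.11-2.12 are not in the available text.

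**Conclusion.** The point holds for Table 2-4 and is minor. As written, the notable-vital-signs table can give a pulse count at 2 of 7 post-baseline visits: Weeks 9 and 12, but not Weeks 2, 4, 8, 16 or 20. One descriptive safety count is affected. No endpoint, test or efficacy conclusion depends on it.

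This rests on three conditions: the footnote is applied literally, pulse is recorded at the examinations in Table 1-2, and the sections not available do not supply an office-pulse criterion.

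The liver wording is a genuine mismatch with protocol Version 02, while SAP Section 4 declares no change from the protocol. It concerns four rows and only participants with a baseline below LLN. The separate liver-function block of Table 2-4 uses multiples of ULN and is unaffected.

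**What to change.** 1. Add a separately labelled office-pulse row to Table 2-4, as the table already does for BP decrease. Keep the 24-hour ABPM mean as its own row, available at Weeks 9 and 12/EOT.
2. Have the sponsor confirm the limits for each source. They need not be equal: for low SBP the table uses <110 mmHg for the office reading and <105 mmHg for the 24-hour mean.
3. Have the sponsor state how unscheduled office pulse is treated. SAP 2.1.1 uses unscheduled values for safety evaluations but excepts ABPM and OBPM, and the available text does not say which rule covers office pulse.
4. In the ALP, ALT, AST and total bilirubin rows, change *abnormal* to *abnormally high*. Protocol Table 10-2 covers only normal and abnormally high baselines, so the sponsor should also state what applies to a low one.

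The cost is a table edit and minor programming before database lock. Office pulse is already due to be summarized and listed, so no new data are needed. The downside is extra isolated flags, for example below 60 bpm in participants on beta blockers, which the rationale for Amendment 1 describes as commonly prescribed in these patients. The documents give no figure for how many.
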